Protocol Title: Near-infrared fluorescence lymphatic imaging to assess improved lymphatic drainage in head and neck cancer survivors after a single- use and two weeks use of the Flexitouch Head and Neck System

Protocol Number and Version: HSC-MS-16-0465; Version 1.10

Principal Investigator: [name]

Co-Investigators: [name]; [name]; [name]

Study Coordinator: [name]

Sponsor: Tactile™ Medical

Population: A total of ten (10) subjects who complete both, over the age of 18, from the patient population at UT Physician’s Otorhinolaryngology Outpatient Clinic who have undergone surgery and/or radiation therapy for treatment of cancer of the head and/or neck

Number of Sites: Single site: UT Physician’s Otorhinolaryngology Outpatient Clinic

Study Duration: Three (3) months

Subject Duration: Twenty-four (24) hours over Two (2) weeks

1.0 General Information

There were nearly 62,000 new head and neck cancer (HNC) cases last year accounting for 3% of all cancers in the US (1) with an increasing incidence among younger adults due to the human papillomavirus (HPV) infection. Treatment is typically surgical resection of primary lesions and extensive lymph node (LN) dissection, followed by fractionated radiation therapy (RT). Because the neck and cervical region contains 1/3 of the body’s LNs (2) surgical disruption of the lymphatic vasculature and LNs together with subsequent RT of the head and neck region results in the debilitating condition of lymphedema and extensive fibrosis in an estimated 75% of all HNC survivors (3, 4). Although the cure rate of these patients is high with extensive LN dissection and RT, the debilitating effects of this treatment significantly reduces the quality of survivorship. HNC lymphedema can have a profound effect on the range of motion, swallowing, and evening breathing.

Unlike breast cancer where a 10% increase in arm volume is used for diagnosis of lymphedema, there is no accepted objective measurement to base the diagnosis of HNC lymphedema. Weight loss and extensive surgery can mask the early signs of edema and lymphedema. As a result, HNC patients/survivors are not screened for lymphedema and early treatment of manual lymphatic drainage to move accumulated tissue fluid and prevent irreversible tissue changes is typically not offered to HNC cancer survivors.

2.0 Background Information

[REDACTED]

[REDACTED]

[REDACTED]

[REDACTED]

[REDACTED]

[REDACTED]

[REDACTED]

3.0 Objectives

The primary objective of the pilot study is to use NIRF imaging to assess whether pneumatic compression can move lymph in HN cancer patients and survivors. The secondary objectives are to assess whether compliant use over a two week period can reverse or reduce the dermal backflow that is associated with HN lymphedema and to collect patient feedback on the ease of use and perception of symptom alleviation with the Flexitouch System and associated head and neck garments after two weeks of daily home use.

The Flexitouch System and associated garments for extremities and trunk are approved for use by patients who are under medical supervision for the treatment of 1) lymphedema (primary or secondary); 2) edema resulting from mastectomies, trauma, sports injuries or post immobilization; 3) venous insufficiencies; 4) wounds and 5) stasis dermatitis, venous stasis ulcers, arterial leg ulcers and diabetic leg ulcers. The variety of garments and accessories available with the Flexitouch system are designed to provide targeted compression therapy to different areas of the body. Tactile Medical™ secured FDA clearance via the 510(k) program to market their newly designed head and vest garments and Flexitouch Treatment Program H1 (Appendix A, p14). When the head garment and vest garment are used together, the resulting compression directs fluid from the head to the axilla in one continuous motion, presumably moving fluid from the head and neck region into the axilla for uptake into the regional lymphatic.

We will assess whether the Flexitouch System can move lymph from the region by using NIRF imaging before and after treatment with the Flexitouch system, as well as, after 2 weeks of compliant home use. We will assess whether Flexitouch usage is associated with alleviation of lymphedema symptoms.

4.0 Study Design

A non-randomized, non-blinded, single site pilot study designed to assess whether NIRF imaging can report on the efficacy of the Flexitouch System used to move lymph in HNC survivors. Specifically, we will assess whether the Flexitouch System can move lymph from the region by using NIRF imaging before and after treatment with the Flexitouch system, as well as, after 2 weeks of compliant home use. Participation will require approximately 24 hours over 2 weeks. Enrollment is targeted to be completed within 3 months.

Assessment of efficacy and safety

[REDACTED]

[REDACTED]

The Flexitouch System, when used for upper and lower extremity lymphedema is a standard-of-care PCD treatment device used routinely in the clinic and for at-home use. In this study, we seek to deploy NIRF imaging to assess the efficacy of the Flexitouch system for moving lymph in HNC survivors and to assess whether this correlates with symptom alleviation. [REDACTED]

[REDACTED]

5.0 Study Population

5.1 Inclusion Criteria

- 1) Participants must be 18 years of age or older
- 2) Participants must be diagnosed with Lymphedema of the Head and/or Neck
- 3) Participants must be diagnosed with squamous cell carcinoma of the oral cavity, oropharynx or larynx and underwent surgery and/or radiation as part of their standard-of-care treatment plan.
- 4) Participants must be ≥ 4 weeks post-radiation therapy
- 5) Female participants of childbearing potential must have a negative urine pregnancy test ≤ 36 hours prior to study drug administration
- 6) Female participants of childbearing potential must agree to use a medically accepted method of contraception for a period of one month after each imaging session
- 7) Participants must be willing to use the Flexitouch[®] System at home daily for two (2) weeks

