5.2 Exclusion Criteria

- 1) Women who are pregnant or breast-feeding
- 2) Persons who are allergic to iodine
- 3) A female of child-bearing potential, who does not agree to use an approved contraceptive for one month after study participation
- 4) Persons who do not meet inclusion criteria
- 5) Persons with pulmonary edema, thrombophlebitis, congestive heart failure, deep vein thrombosis, episodes of pulmonary embolism, infections and inflammation, or acute cancer
- 6) Persons with uncontrolled hyperthyroidism or parathyroidism (for with an endocrinologist recommends against neck compression)
- 7) Carotid sinus hypersensitivity syndrome

- 8) Symptomatic carotid artery disease, as manifested by a recent transient ischemic attack (within 30 days), ischemic stroke, or amaurosis fugax (monocular visual ischemic symptoms or blindness)
- 9) Symptomatic bradycardia in the absence of a pacemaker
- 10) Internal jugular venous thrombosis, acute or within 3 months
- 11) Known intracranial pressure or other contraindication to internal or external jugular venous compression
- 12) Acute radiation dermatitis, unhealed surgical scar, unhealed or open wound(s), surgical flap less than 6-8 weeks post-operative
- 13) Facial or head and neck dermal metastasis
- 14) Acute facial infection (e.g., facial or parotid gland abscess)
- 15) Any condition where increased venous and lymphatic return is undesirable

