6.0 Sample Size/Data Analysis/Subject Withdrawal and Replacement

In this pilot sub-study of a total of ten patients who complete both study visits, we will assess whether there are any changes to lymphatic function after a single use of the pneumatic compression device and after a two week period of daily home use. Five patients will undergo daily ICD of approximately 32 minutes while another five patients will undergo daily ICD of approximately 60 minutes in order to assess the effect of duration on response to therapy. If, after the initial consent and imaging session are completed, a subject withdraws, opts not to complete the daily home therapy (<75% of total treatments), OR does not properly use the device as instructed, they may be dropped from the study cohort and a replacement subject may be enrolled to ensure a full cohort of 10 subjects completes the study.

[REDACTED]

Because this is a pilot study, we cannot statistically power the study for conclusions. Instead we will assess results to visualize trends for a subsequent properly powered study to statistically test the hypothesis that the Flexitouch system can restore lymphatic function.

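### Does inclusion 4 shut out patients who never had radiation, although inclusion 3 admits them?

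*Combined protocol and SAP*

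**What the plan says.** The front page of the combined protocol and SAP describes the population as adult clinic patients "who have undergone surgery and/or radiation therapy for treatment of cancer of the head and/or neck". In Section 5.1, inclusion 3 narrows the cancer to squamous cell carcinoma of three sites but keeps the same treatment wording: patients who "underwent surgery and/or radiation as part of their standard-of-care treatment plan". Inclusion 4 follows: "Participants must be ≥ 4 weeks post-radiation therapy". It has no clause such as 'if irradiated'.

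Two other items in the list do name a subgroup. Inclusion 5 begins "Female participants of childbearing potential must have a negative urine pregnancy test" and inclusion 6 begins "Female participants of childbearing potential must agree to use a medically accepted method of contraception". Section 5.2, exclusion 4, then excludes "Persons who do not meet inclusion criteria".

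On the purpose of the study, Section 6.0 says: "Because this is a pilot study, we cannot statistically power the study for conclusions". Results are to be examined for trends in ten completers, five at each of two daily treatment durations.

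**The concern.** Inclusion criteria apply jointly, so a participant must meet all of them. If inclusion 4 requires every participant to have had radiation, the surgery-only patients admitted by inclusion 3 are removed one line later, and exclusion 4 confirms the removal. If it is only a waiting time, they stay in. The text does not state which is meant.

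Two things would be at stake. The first is compliance: on the strict reading, enrolling a surgery-only patient would need an exception approved in advance by the IRB under Section 12.3, or would be a deviation. The second is description. Section 1.0 attributes lymphedema and fibrosis in these patients to surgical disruption combined with later radiation, so a reader may want to know whether the ten subjects all had both.

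**Working it through.** No sample size, power or error rate enters here, and the plan states no figure to reproduce. The check is to apply the criteria to one kind of patient and see which reading fits the rest of the text.

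**Test case: a patient treated by surgery alone, otherwise eligible.**

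| Statement | Literal reading of inclusion 4 | Waiting-time reading |
|---|---|---|
| Front-page population | in | in |
| Inclusion 3 | met | met |
| Inclusion 4 | not met | not applicable |
| Exclusion 4 | excluded | not triggered |
| Result | ineligible | eligible |

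**Which reading leaves every statement with work to do?**

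- Literal: inclusions 3 and 4 together reduce to 'had radiation, at least 4 weeks ago, with or without surgery'. The surgery-only route in inclusion 3 then admits nobody, and the front page describes a group that the criteria refuse.
- Waiting time: inclusion 3 says which treatments qualify, and inclusion 4 says how long ago any radiation must have been. Nothing is redundant, and the front page agrees.

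The front page is broader than inclusion 3 on tumour type, so it does not stand in for the criteria. On prior treatment, the only matter at issue, the two agree.

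**What the drafting contrast shows.** Of the 7 inclusion criteria, 2 (numbers 5 and 6) name a subgroup and inclusion 4 does not. A pregnancy test or a contraception requirement could be applied to any participant unless the group were named. An interval since radiation has no starting point in a patient who had none, so its wording already suggests whom it concerns. The lists are also loosely drafted: exclusion 4 only restates the inclusion list, and exclusion 6 contains a garbled phrase. A missing qualifier is weak evidence of intent in such text.

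**Size.** Let k be the number of surgery-only patients among the completers. Their share is k/10 of the cohort. One such patient is 1/10 = 10% of the cohort and 1/5 = 20% of one duration group. The documents do not give k. Section 1.0 describes surgery followed by radiation as the typical course, which suggests that k is small but does not fix it.

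**Effect on the analysis.** Section 9.0 defines the quantity of interest as the change in the percentage of area showing dermal backflow, after one session and after two weeks. That is a change within each subject and is defined in the same way whatever the treatment history. The visible text plans no test or powered comparison that the reading could alter.

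**The case for a change.** The strongest case for acting is that eligibility should not depend on interpretation. The authors knew how to restrict a criterion and did so twice. Inclusion 4 opens with the same unrestricted subject as inclusions 1, 2, 3 and 7. Radiation is part of the protocol's own account of the disease, so admitting a never-irradiated patient into a group of five could colour the trend seen there. The remedy would be a few words.

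Part of this stands. The qualifier is absent, no visible passage supplies it, and the eligibility lists show no redaction that might hide it. The mix of treatment histories could also affect the observed changes if response differs by radiation history, though the documents give no figure from which to judge that.

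The rest does not carry. The two readings are not evenly matched, because the literal one defeats the criterion beside it. The deviation scenario arises only on that weaker reading. Nothing in the documents shows that a surgery-only candidate is expected, or that one team at one site would handle such patients inconsistently. Listing each subject's treatment history with the results would be good reporting, but it does not depend on this wording. Parts of Sections 4.0, 6.0 and 9.0 are redacted, so its omission cannot be assumed.

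A reader may also notice that exclusion 12 gives its post-operative flap limit as a range of weeks. That is a separate criterion and does not help to interpret inclusion 4. The same item also covers unhealed scars and open wounds, which partly bridges the range.

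**Conclusion.** The wording gap is real but minor, and no change to the plan is needed. Inclusion 3 and the front-page population both point to inclusion 4 being a waiting time for irradiated patients, and staff would be expected to apply it so. No test, sample size or endpoint definition changes under either reading. The most that can be said of size is 10% of the cohort for each surgery-only completer, with the number of such patients unknown.

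This rests on three assumptions: that the single site applies one reading throughout; that the redacted text does not require radiation of every participant; and that the results are used, as Sections 6.0 and 9.0 say, to look for trends ahead of a properly powered study. If the sponsor did intend to require radiation, the front page and inclusions 3 and 4 would have to be reconciled. Whether never-irradiated patients belong in the population is a clinical decision for the sponsor and investigators, and this review takes no position on it.

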5.2 Exclusion Criteria

- 1) Women who are pregnant or breast-feeding
- 2) Persons who are allergic to iodine
- 3) A female of child-bearing potential, who does not agree to use an approved contraceptive for one month after study participation
- 4) Persons who do not meet inclusion criteria
- 5) Persons with pulmonary edema, thrombophlebitis, congestive heart failure, deep vein thrombosis, episodes of pulmonary embolism, infections and inflammation, or acute cancer
- 6) Persons with uncontrolled hyperthyroidism or parathyroidism (for with an endocrinologist recommends against neck compression)
- 7) Carotid sinus hypersensitivity syndrome

- 8) Symptomatic carotid artery disease, as manifested by a recent transient ischemic attack (within 30 days), ischemic stroke, or amaurosis fugax (monocular visual ischemic symptoms or blindness)
- 9) Symptomatic bradycardia in the absence of a pacemaker
- 10) Internal jugular venous thrombosis, acute or within 3 months
- 11) Known intracranial pressure or other contraindication to internal or external jugular venous compression
- 12) Acute radiation dermatitis, unhealed surgical scar, unhealed or open wound(s), surgical flap less than 6-8 weeks post-operative
- 13) Facial or head and neck dermal metastasis
- 14) Acute facial infection (e.g., facial or parotid gland abscess)
- 15) Any condition where increased venous and lymphatic return is undesirable

5.3 Risks/Discomforts

Near-infrared fluorescence lymphatic imaging

[REDACTED]

Flexitouch® Advance Pneumatic Compression System

Participants enrolled in the sub-study are not expected to be at any higher or additional risk than those who use non-study pneumatic compression devices (PCD), or static compression garments approved for use in head and neck region since pressures do not exceed the pressures of static compression garments. There is risk associated with using any PCD. These risks include, but are not limited to, risk of explosion if the device is used in the presence of flammable gases, risk of electrical shock if the device is immersed in water, or if the housing is broken and subject attempts to service the unit.

5.4 Potential Benefits

While there is no guarantee of a direct benefit to participants, there is a possible benefit of improved lymphatic function and decreased edema with use of the Flexitouch system.

5.5 Cost/Payment

[REDACTED]

[REDACTED]

6.0 Sample Size/Data Analysis/Subject Withdrawal and Replacement

In this pilot sub-study of a total of ten patients who complete both study visits, we will assess whether there are any changes to lymphatic function after a single use of the pneumatic compression device and after a two week period of daily home use. Five patients will undergo daily ICD of approximately 32 minutes while another five patients will undergo daily ICD of approximately 60 minutes in order to assess the effect of duration on response to therapy. If, after the initial consent and imaging session are completed, a subject withdraws, opts not to complete the daily home therapy (<75% of total treatments), OR does not properly use the device as instructed, they may be dropped from the study cohort and a replacement subject may be enrolled to ensure a full cohort of 10 subjects completes the study.

[REDACTED]

Because this is a pilot study, we cannot statistically power the study for conclusions. Instead we will assess results to visualize trends for a subsequent properly powered study to statistically test the hypothesis that the Flexitouch system can restore lymphatic function.

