9.0 Statistics

In this pilot sub-study we will assess whether there are any changes to lymphatic function after a single use of the pneumatic compression device and after a two week period of compliant use.

[REDACTED]

[REDACTED] Specifically, we seek to determine the change in the percentage of area that is demarked by dermal backflow in response to the Flexitouch System use after a single session and after two weeks of compliant use.

[REDACTED]

Because this is a pilot study, we cannot statistically power the study for conclusions. Instead we will assess results to visualize trends for a subsequent properly powered study to statistically test the hypothesis that the Flexitouch system can reduce dermal backflow and restore lymphatic function.

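### The two treatment-duration groups are meant to show the effect of duration, but the split is not randomized, so any difference between them is confounded with who entered each group

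*Combined protocol and SAP*

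**What the plan says.** Section 6.0 plans for ten completers and divides them by length of daily session: "Five patients will undergo daily ICD of approximately 32 minutes while another five patients will undergo daily ICD of approximately 60 minutes". The reason given is "in order to assess the effect of duration on response to therapy". Section 7.0 carries two session lengths into the procedures, and its visible text does not say how a subject comes to receive one or the other.

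Section 4.0 opens with "A non-randomized, non-blinded, single site pilot study".

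Section 3.0 does not list duration among the objectives. "The primary objective of the pilot study is to use NIRF imaging to assess whether pneumatic compression can move lymph" states the primary one, and "The secondary objectives are to assess whether compliant use over a two week period can reverse or reduce the dermal backflow" begins the secondary ones, which also include patient feedback.

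On interpretation, Section 9.0 says "Because this is a pilot study, we cannot statistically power the study for conclusions", and Section 6.0 has the same caveat, followed by "Instead we will assess results to visualize trends for a subsequent properly powered study". On subjects who withdraw, fall below 75% of treatments or misuse the device, Section 6.0 says "they may be dropped from the study cohort and a replacement subject may be enrolled to ensure a full cohort of 10 subjects".

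**The concern.** Assessing the effect of duration is a causal aim that rests on comparing two groups of different people. Without random assignment, the comparison also carries any systematic difference between those people. Eligibility in Section 5.1 leaves room for such differences: three tumour sites, surgery or radiation or both, and any interval of at least 4 weeks since radiation. If the groups were filled one after the other, calendar time would be mixed in as well.

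The results are to be read as trends that inform a later study. A non-random split can produce a trend by duration when there is no effect, or hide one that exists. Telling the reader that the study is small does not warn of this, because low power concerns random error and confounding is systematic.

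**Working it through.** The plan has no power or precision calculation to reproduce. The only stated figure is the total, and 5 + 5 = 10 agrees.

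**Logic.** Section 6.0 sets a between-group causal aim and Section 4.0 excludes randomization. Parts of Sections 4.0, 6.0 and 9.0 are redacted, so an allocation rule may exist there. It could describe or lessen selection, but it could not make the split random without contradicting Section 4.0. The argument rests on the declared non-randomized design and not on the absence of a rule.

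**Illustration of size.** These inputs are assumptions; none is in the documents.

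- Response is normal with within-group SD 1.
- Allocation produces an expected systematic shift of 0.5 to 1.5 SD in a prognostic factor.
- That factor correlates 0.3 to 0.7 with response.
- Duration has no true effect.

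The standard error of a 5 v 5 difference in means is √(1/5 + 1/5) = √0.4 = 0.632 SD. The expected shift in response is the factor shift times the correlation. The probability that the observed difference favours the better-prognosis group is Φ(shift / 0.632).

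| Factor shift (SD) | Correlation | Shift in response (SD) | Probability |
|---|---|---|---|
| 0 | any | 0 | 50% |
| 0.5 | 0.3 | 0.15 | Φ(0.237) = 59.4% |
| 1.0 | 0.5 | 0.50 | Φ(0.791) = 78.5% |
| 1.5 | 0.7 | 1.05 | Φ(1.660) = 95.2% |

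A smaller assumed shift of 0.2 SD with correlation 0.3 gives 0.06 SD and Φ(0.095), about 54%.

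**What randomization would and would not change.** It sets the expected systematic shift to zero. Chance imbalance in a given factor at 5 v 5 remains:

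- P(difference of 0.5 SD or more, either direction) = 2 × [1 − Φ(0.5/0.632)] = 42.9%
- P(difference of 1 SD or more) = 2 × [1 − Φ(1/0.632)] = 11.4%
- mean absolute difference = 0.632 × √(2/π) = 0.505 SD

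The 95% confidence interval for the duration contrast has half-width t(0.975, 8 df) × 0.632 = 2.306 × 0.632 = 1.46 SD, randomized or not.

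**Replacement of subjects.** This is a separate, smaller point. The 75% threshold is relative to each subject's own regimen, so it is neutral if adherence is equal. It could select differently between the groups only if adherence, or the use of the discretion to drop a subject in this open study, differs by duration.

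**The case against.** The case for leaving the plan alone is mainly about weight. Duration is not a listed objective, the hypothesis for the later study concerns use of the system and not session length, and the plan openly declares a non-randomized pilot that looks only for trends. On that view this is one clause needing a caveat. The narrow scope is right and limits the seriousness of the point. But the clause gives the only stated reason for having two groups, and the visible disclaimer is about power.

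A second argument is that randomizing ten people achieves little: imbalance of 0.5 SD or more remains in about 43% of allocations, and the assumed bias lies wholly inside the 1.46 SD half-width. If a true effect of 0.5 SD existed, a randomized trend would still point the wrong way about 21% of the time (1 − Φ(0.5/0.632)). All of this stands. It is why the contrast should be reported descriptively in any case, and why correcting the wording alone is an acceptable fallback. It does not justify keeping a systematic error that can be removed at almost no cost.

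Third, the probabilities above depend on assumed shifts and on the sign of a mean difference only. At small shifts the effect is close to a coin toss, and a 95% confidence interval would exclude zero far less often: about 11% of the time for a difference of 0.5 SD and 29% for 1.0 SD. That is fair, and the figures should be read as illustration. A single clinic with a 3-month enrolment target also limits differences by site and calendar time, though it does not exclude selection.

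Fourth, the outcome in Section 9.0 is a within-patient change, so stable differences in level cancel. Factors that modify the change do not cancel, and prior treatment or time since radiation could plausibly be among them.

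Finally, redacted text may contain matching, adjustment or a further caveat. Remarks on what the plan omits therefore apply to the visible text only. None of these would turn the split into a randomized one.

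**Conclusion.** The concern holds. As designed, the study cannot support a statement about the effect of session duration, because the contrast is confounded with selection into the groups. This follows from two explicit statements in the protocol and needs no numerical assumption.

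Its size cannot be derived from the documents. For selection shifts in response of 0.15 to 1.05 SD, the chance of a trend toward the better-prognosis group with no duration effect is 59% to 95%, and this range depends entirely on the assumed shift and correlation. The harm is limited to conclusions about duration. The before/after assessments after a single use and after two weeks are not affected. The point should be corrected, but it does not threaten the main purpose of the study.

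**What to change.** Preferred: allocate subjects 5:5 to the two durations already in the protocol from a pre-generated, concealed random list, opened only after eligibility is confirmed. Amend Sections 4.0 and 6.0 to say so, and keep the 5:5 split when a subject is replaced. Present the duration contrast as descriptive, with its 95% confidence interval.

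Fallback, if enrolment is too far advanced: describe the groups as non-randomized cohorts and remove the stated aim of assessing the effect of duration.

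In either case it would help to report every dropped subject by assigned group, with sessions completed and the reason.

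The cost is one allocation list, wording changes in two sections, and an IRB amendment approved before implementation, as Section 12.3 requires. No patients or procedures are added. The downsides are that subjects and staff can no longer choose the duration, a replacement's group may be guessable in an open study, and chance imbalance remains. The fallback needs only the amendment.

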7.0 Study Procedures

The sub-study consists of two NIRF lymphatic imaging sessions (see Section below for NIRF procedure) separated by approximately two (2) weeks. At each session, measurements of the subject's head and neck will be recorded and 3D images and/or digital photographs will be taken before and after treatment. Participants will don the head and neck and vest garments before undergoing Treatment Program H1 with the Flexitouch System. Imaging with NIRFLI system will

occur before, during and after treatment with the Flexitouch System. The first NIRF lymphatic imaging session will establish the presence of lymphatic dysfunction as visualized with the NIRFLI System. The subject will be loaned the Flexitouch® Advanced Pneumatic Compression system along with the Head Garment and Vest for Head & Neck. The subjects will be instructed in the proper fitting of the garments and the use of the Flexitouch system. The subjects will complete the Flexitouch Treatment Program H1 (~30-40 minutes or ~60 minutes) daily for approximately two (2) weeks. Participants will be asked to keep a diary of their daily use on the Flexitouch System. After approximately two (2) weeks of daily use, the subject will return for the second and final NIRF lymphatic imaging session, at which time they will return the Flexitouch System and associated garments to the research team. Subjects will then be asked a series of questions related to the ease of use of the Flexitouch System and their perception of the treatment they received while using the Flexitouch System.

NIRF Lymphatic Imaging

[REDACTED]

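### Section 6.0 describes one cohort of completers for both the single-use and the two-week change, so first-session data already collected may be dropped because of later home-use problems

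*Combined protocol and SAP*

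**What the plan says.** Section 3.0 sets the main question: "The primary objective of the pilot study is to use NIRF imaging to assess whether pneumatic compression can move lymph". Reversing or reducing dermal backflow over two weeks of compliant use is a secondary objective.

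Section 6.0 describes the subjects in whom change is assessed as "ten patients who complete both study visits, we will assess whether there are any changes to lymphatic function after a single use", and the same sentence goes on to the two-week period. Five subjects are to have about 32 minutes daily and five about 60 minutes. The removal rule opens with "If, after the initial consent and imaging session are completed, a subject withdraws". It adds a second ground, fewer than 75% of home treatments, and then gives the third ground together with the consequence of all three: if the subject "does not properly use the device as instructed, they may be dropped from the study cohort". It continues that "a replacement subject may be enrolled to ensure a full cohort of 10 subjects completes the study".

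Section 7.0 says that imaging will "occur before, during and after treatment with the Flexitouch System" and describes two such sessions about two weeks apart. Section 9.0 names the outcome as the change in the percentage of area showing dermal backflow, once after a single session and once after two weeks. It attaches the compliance condition to the two-week change only and does not mention completers. Parts of both 6.0 and 9.0 are redacted.

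**The concern.** The change after a single use is fully measured when the first session ends. All three grounds for removal arise afterwards. They bear on whether a subject can inform the two-week question, but not on whether the first treatment moved lymph. If the 6.0 cohort is used for both questions, a condition that belongs to the secondary objective is carried over to the primary one.

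Two things are then at stake. First, usable observations are lost from a very small study. Second, the subjects who remain have been selected by what they did after the outcome was recorded, in a non-blinded study (4.0) where removal is discretionary. If early response is related to later adherence, the single-use trend in the final ten will differ from the trend in everyone treated. The plan means these trends to inform a later powered study, so it should be clear whose data they summarise.

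**Working it through.** **The plan's own figure.** 5 subjects at about 32 minutes + 5 at about 60 minutes = 10, which matches the stated cohort. The visible text has no power calculation, standard deviation, effect size or drop rate, so there is nothing further to reproduce.

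**Order of events.**
1. First session: images before, during and after treatment (7.0). The single-use change can be computed from here on.
2. Home use: daily for about two weeks. If that means 14 treatments, 75% is 0.75 × 14 = 10.5, so a subject needs at least 11.
3. Removal for withdrawal, low use or improper use (6.0). Each ground comes after step 1.
4. Second session, then replacement as needed until ten complete.

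A subject can attend both sessions and still be removed for low or improper use.

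**Size of the loss.** Let d be the number dropped after the first session and replaced. Then N = 10 + d subjects have single-use data. The documents give no d; I assume 1 to 3.

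- Share left out = d/N.
- Increase in the standard error of the mean change from using 10 rather than N = √(N/10) − 1, assuming the same standard deviation in dropped and retained subjects.
- Shift in the mean from omitting the dropped subjects = (d/N) × Δ, where Δ is the difference between completers and dropped subjects in mean single-use change. Assumed size of Δ: 0.5 to 1.0 SD, in either direction.

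| d | N | Left out | Standard error larger by | Shift, Δ = 0.5 SD | Shift, Δ = 1.0 SD |
|---|---|---|---|---|---|
| 0 | 10 | 0% | 0% | 0 | 0 |
| 1 | 11 | 1/11 = 9.1% | √1.1 − 1 = 4.9% | 0.05 SD | 0.09 SD |
| 2 | 12 | 2/12 = 16.7% | √1.2 − 1 = 9.5% | 0.08 SD | 0.17 SD |
| 3 | 13 | 3/13 = 23.1% | √1.3 − 1 = 14.0% | 0.12 SD | 0.23 SD |

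If Δ = 0, only precision is lost. Nothing in the documents indicates the sign of Δ.

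**Sections 6.0 and 9.0 side by side.** 6.0 puts the completer phrase in front of both changes. 9.0 states the same aim without it and makes compliance a condition of the two-week change alone. Neither visible section says what happens to the first-session data of a dropped subject.

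**The case against.** The strongest reply is that 6.0 never says single use will be assessed only in completers. Its opening phrase can be read as the recruitment target, as on the Population line of the protocol summary, and the replacement rule serves the headcount of ten. Section 9.0, which is the statistics section, is compatible with using every first session. Redacted blocks sit in both sections, where evaluability rules would naturally appear. This stands. A reader might infer that the plan excludes first-session data of dropped subjects, but the documents do not support that: the text permits the exclusion and does not visibly prevent it.

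Lymph movement is also imaged at the second session, so the primary objective does not rest on the first session alone. One fixed cohort also lets the same subjects contribute to both time points and to the comparison of durations. That is a fair reason to show the completers, but not to show only them.

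The study is an unpowered pilot looking for trends, and no test or decision rule changes. That limits the importance of the point.

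Two stronger readings are tempting. One is that the single-use trend will look too favourable, because subjects who noticed no effect would stop. The documents give no evidence on who stops or why, so the direction is unknown. The other is that the objective to "collect patient feedback on the ease of use and perception of symptom alleviation" is biased, because those who struggle with the device can be replaced. But 3.0 defines that feedback as following two weeks of daily home use, 7.0 places it at the second session ("Subjects will then be asked a series of questions related to the ease of use of the Flexitouch System"), and nothing visible bars asking a non-compliant subject who attends. I do not rest the point on either.

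**Conclusion.** The point holds in a limited form. As visibly written, 6.0 uses one cohort of completers for two questions that need different ones, and it allows valid single-use data to be set aside for reasons that arise later. Section 9.0 does not carry the restriction over, and redacted text may already resolve it.

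The size depends on a drop count that the documents do not give: for 1 to 3 drops, 9% to 23% of subjects with single-use data and a standard error about 5% to 14% larger. Any selection bias could go either way; under the assumed differences it is about 0.05 to 0.23 SD. If nobody is dropped, or if dropped subjects' first sessions are kept, there is no loss. The two-week analysis in compliant subjects is the plan's stated aim and is not in question. This is worth considering; it does not threaten the study.

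**What to change.** In 6.0 and 9.0, state the following:

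1. The single-session change is summarised in every subject with a completed first imaging session, including any later dropped or replaced.
2. The two-week change is summarised in the compliant completers, as now intended.
3. Removals are decided from the diary (12.4) before the second-session images are read, with the ground recorded.
4. The number of removals and the reasons are reported by duration group.

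If redacted text already keeps the first-session data, a cross-reference in 6.0 covers the first item.

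The cost is about four sentences, with no extra imaging and no change to the target of ten completers. The downside is that the single-use and two-week results may rest on different numbers of subjects. Showing the single-use result in the ten completers as well keeps the two comparable.
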